**9.2.5. Imputation of Partial Dates**

Imputed partial dates will not be used to derive study day, duration (e.g., duration of adverse events), or elapsed time variables. In addition, imputed dates are not used for deriving the last contact date in overall survival analysis dataset.

With the exception of new anti-cancer start date on the Oncology time to event analysis dataset and exposure end date on the Exposure analysis dataset, imputed dates will also not be stored on datasets.

Imputed dates will not be displayed in listings. However, where necessary, display macros may impute dates as temporary variables for the purpose of sorting data in listings only. In addition partial dates may be imputed for specific analysis purposes as outlined below.

The partial date imputation will follow ADaM conventions. The ADaM approach is to populate the numeric date variables with the imputed date and add a flag variable to the dataset that indicates the level of imputation.

The flag variable can contain the values: blank, 'D', 'M', 'Y'.

blank: indicates that no imputation was done

D='Day': indicates that the day portion of the date is imputed

M='Month': indicates that the month and day portions of the date are imputed

Y='Year': indicates that the entire date (year, month, and day) is imputed

Example of Date Variables:

XYZD\_ - character date variable

XYZDT - numeric date variable

XYZDTFL - flag variable

Details on imputing partial dates for specific datasets follow.

**Adverse Events (AE):**

Imputations in the adverse events dataset are used for slotting events to the appropriate study time periods and for sorting in data listings.

Dataset	Date	Missing Element	Rule

Dataset	Date	Missing Element	Rule
Adverse Events (AE)	Start Date	day, month, and year	
 
No Imputation for completely missing dates
 

		day, month	
 
If study treatment start date is missing (i.e. subject did not start study treatment), then set start date = January 1.
 
Else if study treatment start date is not missing:                             
 
If year of start date = year of study treatment start date then                                     
 
If stop date contains a full date and stop date is earlier than study treatment start date then set start date = January 1.
 
Else set start date = study treatment start date.
 
 
 
Else set start date = January 1.
 
 
 

		day	
 
If study treatment start date is missing (i.e. subject did not start study treatment), then set start date = 1st of month.
 
Else if study treatment start date is not missing:                             
 
If month and year of start date = month and year of study treatment start date then                                     
 
If stop date contains a full date and stop date is earlier than study treatment start date then set start date = 1st of month.
 
Else set start date = study treatment start date.
 
 
 
Else set start date = 1st of month.
 
 
 

	End Date		
 
No imputation for partial end dates will be performed
 

**Anti-Cancer Therapy and Radiotherapy:**

Start and end dates are generally not imputed. [REDACTED]

[REDACTED]

Imputed partial dates will not be used to derive time since most recent prior therapy. In addition, the cancer therapy treatment status variable, and not any variables that use imputed partial dates, will be used to differentiate prior and follow-up anti-cancer therapy and radiotherapy.

Dataset	Date	Missing Element	Rule
Anti-Cancer Therapy Radiotherapy	Start Date	day, month, and year	
 
No Imputation for completely missing dates
 

		day, month	
 
If partial date contains a year only set to January 1st.
 

		day	
 
If partial date contains a month and year set to the 1st of the month.
 

	End Date		
 
No imputation for partial end dates will be performed
 

### Surgery:

The date of surgery or procedure is generally not imputed. However, post treatment surgery or procedure dates maybe imputed (if necessary) to determine date of new anti-cancer therapy. In this case only, the date of new anti-cancer therapy (not specific surgery or procedure date) will be stored on appropriate efficacy datasets. The category for surgical procedure variable, and not any variables that use imputed partial dates, will be used to differentiate prior, on, and follow-up surgical procedure data. The derived time in relation to treatment variables are not needed for reporting of data because the category for surgical procedure variable can be used. Therefore, imputed dates are not needed for derivation of time in relation to treatment.

Dataset	Missing Element	Rule
Surgical Procedures	day, month, and year	
 
No Imputation for completely missing dates
 

	day, month	
 
If partial date contains a year only set to January 1st.
 

	day	
 
If partial date contains a month and year set to the 1st of the month
 

### Concomitant Medication and Blood and Blood Supportive Care Products:

Start and end dates for use in derivation of the reference variables for concomitant medication start and end relative to treatment will be imputed. Similarly start and end dates for use in derivation of the reference variables for blood and blood supportive care start and end relative to treatment will be imputed. However these imputed start and end dates will not be stored permanently in the analysis datasets.

The reference variables will be used to differentiate before, during and after for the concomitant medication or blood or blood supportive care start and end dates. The derived time in relation to treatment variables are not needed for reporting of these data.

Dataset	Date	Missing Element	Rule
Concomitant Medication  Blood and Blood Supportive Care Products	Start Date	day, month, and year	
 
• No Imputation for completely missing dates
 

		day, month	
 
• If study treatment start date is missing (i.e., subject did not start study treatment), then set start date = January 1.
 
• Else if study treatment start date is not missing: 
 
○ If year of start date = year of study treatment start date then 
 
▪ If stop date contains a full date and stop date is earlier than study treatment start date then set start date = January 1.
 
▪ Else set start date = study treatment start date.
 
 
 
○ Else set start date = January 1.
 
 
 

		day	
 
• If study treatment start date is missing (i.e. subject did not start study treatment), then set start date = 1st of month.
 
• Else if study treatment start date is not missing: 
 
○ If month and year of start date = month and year of study treatment start date then 
 
▪ If stop date contains a full date and stop date is earlier than study treatment start date then set start date= 1st of month.
 
▪ Else set start date = study treatment start date.
 
 
 
○ Else set start date = 1st of month.
 
 
 

	End Date	day, month, and year	
 
• No Imputation for completely missing dates
 

		day, month	
 
• If partial end date contains year only, set end date = earliest of December 31 or date of last contact.
 

		day	
 
• If partial end date contains month and year, set end date = earliest of last day of the month or date of last contact (MSTONE.LCONTDT).
 

**Time to Event, Response, and Response for Independent Review:**

Start dates for follow-up anti-cancer therapy, radiotherapy (where applicable), and surgical procedures (where applicable) will be temporarily imputed in order to define event and censoring rules for progression-free survival; intracranial, extracranial, and overall response rate; and duration of intracranial, extracranial, and overall response (i.e., start date for new anti-cancer therapy). Dates will only be imputed when a month and year are available but the day is missing. The imputed date(s) will not be stored on the anti-cancer therapy, radiotherapy, or surgical procedure datasets. The following rules will be used to impute the date when partial start dates are present on anti-cancer therapy radiotherapy, and/or surgical procedures dataset[s]:

Dataset	Date	Missing Element	Rule
Anti-Cancer Therapy  Where applicable:  Radiotherapy  Surgical Procedures	Start Date	day, month, and year	
 
No Imputation for completely missing dates
 

		day, month	
 
No imputation for missing day and month (note the eCRF should only allow for missing day)
 

		day	
 
If partial date falls in the same month as the last dose of study treatment, then assign to earlier of (date of last dose of study treatment+1, last day of month).
 
If partial date falls in the same month as the subject's last assessment and the subject's last assessment is PD, then assign to earlier of (date of PD+1, last day of month).
 
If both rules above apply, then assign to latest of the 2 dates
 
Otherwise, impute missing day to the first of the month.
 

	End Date		
 
No imputation for partial end dates will be performed
 

The date of new anti-cancer therapy is derived as the earliest date of new anti-cancer therapy (e.g., chemotherapy), radiotherapy (where applicable), or a cancer-related surgical procedure (where applicable) and will include imputed dates. If the date of new anti-cancer therapy is an imputed date, then the date of new anti-cancer therapy flag variable is assigned the value of 'D' to indicate that the day portion of the date is imputed (following ADaM convention).

As multiple dates are used to derive the date of new anti-cancer therapy ensure that the date of new anti-cancer therapy flag is only set to 'D' if the derived date is imputed. For example if the date of new radiotherapy is imputed but the date of new anti-cancer therapy is prior to date of new radiotherapy and the new anti-cancer therapy date is not a partial date then the flag should be set to missing as the date used for the new anti-cancer therapy is not an imputed date.

### **9.2.6. Imputation of Missing Exposure End Dates**

The rules for imputing missing exposure end dates given in this section apply to both dabrafenib and trametinib. The study treatment end date variable will hold the last date of exposure for either dabrafenib or trametinib, that is, the latest exposure end date across all study treatments.

In general, completely missing dates are not imputed. However, subjects in oncology trials may still be on study treatment when analyses are performed and so may have missing exposure end dates in their last dosing record. Missing exposure end dates for subjects who are still on study treatment at the time of an analysis will be imputed. For subjects with missing exposure end dates at the time of data cutoff, the exposure end date will be imputed to the earliest of: the date of the data cutoff, the date of withdrawal from the study, or the death date. The imputed exposure end date will be used to calculate cumulative dose and exposure duration. The imputed exposure end date will be stored in the exposure analysis dataset and an exposure end date imputation flag variable will be derived indicating which exposure end date records are imputed. Imputed exposure end dates will also be stored on the study treatment end date variable.

For subjects who have missing end dates in their last exposure record because they are still on study treatment, the on-therapy indicator variables (time in relation to study treatment) are assigned to on-therapy for all records where the 'dataset'.date' is after or on the study treatment start date.

### **9.2.7. Baseline Definition**

Baseline will be defined as the most recent, non-missing value prior to or on the first study treatment dose date. For laboratory data, baseline will be defined as the most recent, non-missing value from a central laboratory prior to or on the first study treatment dose date. If there are no central labs collected for a subject and lab test prior to or on the first dose of study treatment, the most recent, non-missing value from a local laboratory prior to or on the first dose of study treatment will be defined as the baseline value.

For subjects who did not receive study treatment during the study, baseline will be defined as the latest, non-missing collected value.

### 9.2.8. Change from baseline

Change from baseline will be presented for safety data as described in Section 12.

Change from baseline is calculated as:

- For records occurring after baseline: (visit value) – baseline value.

Percent change from baseline is calculated as:

- For records occurring after baseline: ((change from baseline) / baseline value) \* 100

If either the baseline or visit value is missing, the change from baseline and/or percent change from baseline is set to missing as well.

### 9.2.9. Multiple Assessments

All data will be reported according to the nominal visit date for which it was reported (that is, no visit windows will be applied during dataset creation). Unscheduled data will only be included in the display sections that report worst- case post-baseline.

If multiple assessments on different days are reported for the same scheduled assessment, then the earliest assessment for that scheduled assessment will be analyzed.

If multiple assessments are reported on the same date for the same scheduled planned time, then the worst-case result will be analyzed, with the exception of laboratory data reported from both central and local laboratories. If laboratory data is reported from both central and local laboratories with the same date, then the central laboratory data will be analyzed to provide consistency with measurements from other subjects.

Data from all assessments (scheduled and unscheduled), including multiple assessments, will be included in listings.

### 9.2.10. Actual Treatment

The subjects' actual treatment will be derived from exposure data. If a subject's actual treatment is the same as the assigned treatment, then actual treatment is the assigned treatment. If a subject receives a study treatment that is different from the assigned treatment for the entire time of treatment, then actual treatment is the treatment actually received.

### 9.2.11. Extended Loss to Follow-up or Extended Time without an Adequate Assessment

If two or more consecutive scheduled disease assessments are missed and are then followed by an assessment of PD or death, PFS will be censored at the last adequate assessment prior to PD or death. When the scheduled disease assessment is every 8 weeks, a window of 119 days (16 weeks + 7 day window) will be used to determine whether there was an extended time without adequate assessment. That is, if the time difference between the PFS event of PD or death and the last adequate assessment is

more than 119 days, then PFS will be censored at the last adequate assessment prior to the PFS event. If the Week 4 and Week 8 disease assessments are both missed or are inadequate (that is, the first adequate disease assessment is at Week 16), and the Week 16 disease assessment shows progressive disease, then PFS will be set to Day 1.

#### **9.2.12. Date Associated with Response**

For each disease assessment after baseline, determine the dates associated with intracranial, extracranial, and overall response. For any type of complete response (CR) or partial response (PR), assign to the latest date within the disease assessments. For any type of stable disease (SD), Non-CR/Non-PD or Not Evaluable, assign to the earliest date within the disease assessments. For any type of progressive disease (PD), assign to the earliest assessment date associated with the progression.

#### **9.2.13. Cardiac Scan Modalities (ECHO/MUGA)**

The same modality (ECHO or MUGA) for determining cardiac scan data (e.g., left ventricular ejection fraction (LVEF)) should be used to follow a subject throughout the study. The absolute change from baseline values will not be calculated for any subjects where the post-baseline value was determined by a cardiac scan modality that is different than the one used to determine baseline value.

#### **9.2.14. Derived and Transformed Variables**

See Section 11 for details on analyses for intracranial, extracranial, and overall response, progression-free survival, overall survival, duration of intracranial response, duration of extracranial response, and duration of overall response.

#### **Prognostic Factors**

The prognostic variables below will be added to the following datasets to support exploratory analyses: ADSL, demography, overall response, overall response independent review (if there is independent review), and time to event datasets.

Baseline ECOG performance status: Baseline ECOG performance status can be 0, 1, or 2, depending on cohort. Assign the baseline ECOG performance status value.

Visceral Disease at baseline can be yes or no; assign as follows:

1 = Yes

0 = No

Number of extracranial disease sites at baseline (will be adjusted based on the distribution of the data if appropriate). Sum the number of unique sites of disease at screening and assign as follows:

1 = More than 3

0 = 2 or fewer

Number of intracranial target lesions at baseline (will be adjusted based on the distribution of the data if appropriate). Sum the number of intracranial target lesions at screening and assign as follows:

4 = 5

3 = 4

2 = 3

1 = 2

0 = 1

Number of intracranial non-target lesions at baseline (will be adjusted based on the distribution of the data if appropriate). Sum the number of intracranial non-target lesions at screening and assign as follows:

4 = 5 or more

3 = 4

2 = 3

1 = 2

0 = 1

Gender covariate: Assign

1 = Female

0 = Male

AGE (continuous)

Age at baseline categorized as follows:

1 = More than 65 years old

0 = No more than 65 years old

The time since initial diagnosis of intracranial disease to treatment category:

1 = At least 1 year

0 = Less than 1 year

The time since initial diagnosis of extracranial disease to treatment category:

1 = At least 1 year

0 = Less than 1 year

Race categorized as follows:

2 = Other

1 = African-American

0 = White

Censoring Date for Progression Free Survival and Duration of Intracranial, Extracranial, and Overall Response

Date of new anti-cancer therapy flag: If the date of new anti-cancer therapy is an imputed date, then set to 'D'. Otherwise set to missing. See Section 9.2.5 for specific rules for imputing partial dates. As multiple dates are used to derive the date of new anti-cancer therapy ensure that the flag is only populated if the derived date is imputed. For example, if the date of new radiotherapy is imputed but the date new anti-cancer therapy is prior to date of new radiotherapy and the new anti-cancer therapy date is not a partial date then the flag should be set to missing as the date used for the date of new anti-cancer therapy is not an imputed date.

### **9.2.15. Cut-off date**

The analysis cut-off date for the primary analysis of study data will be established. The primary efficacy analysis will be performed when all subjects in cohort A have had the opportunity for three (3) post baseline disease assessments. All statistical analyses will be performed using all data collected in the database up to the data cutoff date. All data with an assessment date or event start date (e.g. vital sign assessment date or start date of an adverse event) prior to or on the cut-off date will be included in the analysis. Any data collected beyond the cut-off date will not be included in the analysis and will not be used for any derivations. All events with start date before or on the cut-off date and end date after the cut-off date will be reported as 'ongoing'. The same rule will be applied to events starting before or on the cut-off date and not having documented end date. This approach applies, in particular, to adverse event and concomitant medication reports.

## **9.3. Study Time Periods**

### **9.3.1. Time in Relation to Treatment**

Adverse events, serious adverse events, death, laboratory data, vitals, ECG, and ECHO/MUGA data will be assigned to the study time periods defined below. Partial dates will be imputed into full dates, if applicable, for slotting data to the appropriate

categories below (see Section 9.2.5). Flag variables (time in relation to study treatment) indicating the study time periods will be added to these datasets.

**Pre-therapy** is defined as the time prior to the subject's first dose of study treatment.

**On-therapy** is defined as the time from first dose of study treatment to 30 days after the last dose date of study treatment.

**Extension** is defined as the time from overall progression + 1 day to the last dose date of study treatment.

**Post-therapy** is defined as any time beyond the on-therapy period if study treatment stops then, or after the extension period if study treatment is continued beyond initial progression.

Some datasets include the first dose day as On-therapy and some exclude the first dose date as On-Therapy. The first dose day (Day 1) is considered pre-therapy for ECOG, ECG, vital signs, liver events, lab tests, and cardiac scan. The first dose day (Day 1) is considered to be On-therapy for adverse events and concomitant medications.

### 9.3.2. Study Time Periods for Concomitant Medications and Blood and Blood Supportive Care Products

Concomitant Medication and Blood and Blood Supportive Care Product start and end dates will be assigned to study time periods in relation to first dose of study treatment as defined below. The start date references time flag variables and end date reference time flag variables will be added to the concomitant medications and blood and blood supportive products datasets, respectively.

- **Start relative to treatment:** Assign to 'BEFORE' if start date is prior to study treatment start date or if subject has not taken any study treatment or (start date is missing and end date is before study treatment start date). Else assign to 'DURING' if the start date falls into the on-therapy period as defined above or if subject is ongoing (not all study treatment discontinuation records completed) or start date is missing. Else assign to 'AFTER' if start date is after the on-therapy period.
- **End relative to treatment:** Assign to 'BEFORE' if end date is prior to study treatment start date or if subject has not taken any study treatment. Else assign to 'DURING' if start date falls into the on-therapy period or if subject is ongoing (not all study treatment discontinuation records completed) or (end date is missing and start relative to treatment not 'AFTER'). Else assign to 'AFTER' if start date is after the on-therapy period or (end date is missing and start relative to treatment='AFTER').

Only on-therapy blood and blood supportive care products that start after the start of study treatment are included in the Blood Products and Blood Supportive Care Product summaries. Therefore, for summary tables, include blood and blood supportive care product records where start relative to treatment in ('DURING') and end relative to treatment in ('DURING','AFTER'). All data will be reported in listings.

Concomitant medication start relative to treatment and end relative to treatment flags are used to select data to include in the Concomitant Medication summaries as follows:

- **Summary of Concomitant Medications:** This summary will contain medications including those with start date prior to study treatment start date and continue (missing end date or end date after study treatment start date) on therapy. Note that any medications with start date and end date prior to study treatment start date will be excluded as they are not concomitant. In addition, any medication that was started during post-therapy will be excluded. Include concomitant medication records where start relative to treatment in ('BEFORE','DURING') and end relative to treatment in ('DURING','AFTER').

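### SAP 9.3.2: the end-of-medication flag tests the start date, so drugs begun before first dose and stopped on or after it drop out of the concomitant medication summary once a subject is off treatment

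*SAP*

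**What the plan says.** SAP 9.3.2 derives two flags per record, one for the start and one for the end of the medication, each relative to study treatment.

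- **Start flag.** "Assign to 'BEFORE' if start date is prior to study treatment start date or if subject has not taken any study treatment". A drug already in use at first dose therefore has start flag BEFORE.
- **End flag, BEFORE.** "Assign to 'BEFORE' if end date is prior to study treatment start date or if subject has not taken any study treatment". This branch uses the end date.
- **End flag, DURING.** "Else assign to 'DURING' if start date falls into the on-therapy period or if subject is ongoing". A further clause covers records where the "end date is missing and start relative to treatment not 'AFTER".
- **End flag, AFTER.** "Else assign to 'AFTER' if start date is after the on-therapy period or (end date is missing", the last clause applying where the start flag is AFTER.

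A subject counts as ongoing while not all treatment discontinuation records are complete. SAP 9.3.1 defines the on-therapy period as "the time from first dose of study treatment to 30 days after the last dose date of study treatment", and counts Day 1 as on-therapy for concomitant medications.

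For the summary table, 9.3.2 first states the content in words. Drugs that started before treatment and carried on into it are in, whether they have no end date or one after treatment start. Drugs with both dates before treatment are out, as are drugs begun post-therapy. It then gives the filter: "Include concomitant medication records where start relative to treatment in ('BEFORE','DURING') and end relative to treatment in ('DURING','AFTER").

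**The concern.** A flag that is meant to place the end of a medication in time uses a recorded end date only to decide whether the drug stopped before treatment. After that it looks at the start date. For a drug begun before first dose, the start date can never fall in or after the on-therapy period, so neither remaining date test can be met.

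At stake is the accuracy of Table 1.5010. Cohorts A to C may enter on a stable or decreasing corticosteroid dose, and Cohort D on corticosteroids without dose stability (Protocol Section 3). A pre-existing steroid stopped on study is therefore a possible example of a lost record. The loss would also depend on treatment status: the rule keeps a record for a subject still on treatment and drops the identical record once discontinuation is documented. Under SAP 14.1.1 the table is produced at both the interim and the primary analysis, so the two versions could differ for this reason alone.

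**Working it through.** No figure in the plan can be reproduced here; the check is a logical one. The start flag, end flag and filter were coded as written and run over the possible start/end combinations. The same run was repeated with the DURING and AFTER tests of the end flag using the end date.

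**Inputs (illustrative days, first dose = 0).** Last dose is day 200, so the on-therapy period ends on day 200 + 30 = 230. Starts: before = −20, during = 50, after = 260. Ends: before = −5, during = 100, after = 300, or missing.

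**Key case: off treatment, start −20, end 100.**

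1. Start flag: −20 < 0, so BEFORE.
2. End flag BEFORE? 100 is not before 0. No.
3. End flag DURING? The start, −20, is not within 0 to 230; the subject is not ongoing; the end date is not missing. No.
4. End flag AFTER? −20 is not after 230; the end date is not missing. No.
5. No flag is assigned. The filter needs DURING or AFTER, so the record is excluded.

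**All combinations, subject off treatment.**

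| Start | End | Start flag | End flag as written | In table? | End flag using end date | In table? |
|---|---|---|---|---|---|---|
| before | before | BEFORE | BEFORE | no | BEFORE | no |
| before | during | BEFORE | none | **no** | DURING | **yes** |
| before | after | BEFORE | none | **no** | AFTER | **yes** |
| before | missing | BEFORE | DURING | yes | DURING | yes |
| during | during | DURING | DURING | yes | DURING | yes |
| during | after | DURING | DURING | yes | AFTER | yes |
| during | missing | DURING | DURING | yes | DURING | yes |
| after | after | AFTER | AFTER | no | AFTER | no |
| after | missing | AFTER | AFTER | no | AFTER | no |

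Two rows are wrongly excluded as written, and both are restored when the end date is used. One further row (during/after) changes its label but stays in the table. The last column agrees with the content that 9.3.2 describes in words.

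**Subject ongoing.** The before/during record takes DURING from the clause "if subject is ongoing (not all study treatment discontinuation records completed") and is included. The same record, with the same dates, is excluded once the discontinuation records are complete.

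**Blood products.** That summary requires start flag DURING, so no record with start flag BEFORE enters it under either version. Its membership is the same in every row.

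**The case against.** The intent is clear elsewhere. The wording in 9.3.2 says these drugs are included. SAP 9.2.5 says the reference variables separate before, during and after for both start and end dates, and it imputes partial end dates for that purpose. SAP 9.2 leaves full derivation detail to separate dataset specifications, which are not available here, and unassigned flags might be noticed in programming checks. This stands in part: the loss occurs only if the text is programmed literally. But clear intent elsewhere confirms the contradiction and does not remove it. If the code already uses the end date, the SAP misdescribes it.

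Four stronger readings might be inferred, and the documents do not support them.

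- **Most subjects are affected.** The protocol's amendment rationale reports 9 patients still on treatment; against about 120 planned, (120 − 9)/120 = 92.5% would be off treatment. That is the share of planned subjects exposed to the rule at that date, not the share who lose a record. It is also not tied to the SAP's data cut-off.
- **Tapered steroids necessarily disappear.** SAP 10.5 counts a subject once per ingredient. If a lower dose is entered as a new record starting on therapy, that record is flagged DURING and the subject stays counted. How dose steps are recorded is not stated.
- **Anti-epileptics are widely lost.** Protocol Section 3 bars prophylactic anti-epileptics in Cohorts A to C, except for a pre-existing condition unrelated to brain metastasis. They are generally allowed only in Cohort D, with 15 planned subjects.
- **Intracranial response results are distorted.** Response is derived from lesion assessments (SAP 11.1), no covariate analysis is planned (8.2), and the only planned subgroups are for adverse events (8.3).

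**Conclusion.** The rule is wrong as written and contradicts the table content stated in the same section. For subjects whose treatment discontinuation records are complete, every medication record that began before first dose and has a recorded stop on or after first dose, whether during or after the on-therapy period, gets no end flag and is left out of Table 1.5010. Pre-existing drugs with no end date are kept.

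The size in subjects cannot be derived. A subject is lost for an ingredient only if no other record of that ingredient qualifies, and the documents give no count of such cases. The direction is certain: any error is an undercount, and it can grow as subjects come off treatment.

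The consequence is limited to one descriptive table. By-subject listings keep the records, and no efficacy result uses the flag. The conclusion assumes that the derivation follows the SAP text literally. The correction should be made because the contradiction is plain and the remedy trivial.

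**What to change.** In the end-flag rule of SAP 9.3.2, replace *start date* with *end date* in two places: the DURING test for falling in the on-therapy period, and the AFTER test for lying beyond it. Leave the ongoing and missing-end-date clauses as they are. Then check the analysis dataset specification and the program for Table 1.5010 against the corrected rule, and look for concomitant medication records with a blank end flag. If a version of the table has already been produced, rerun it if such records exist.

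Medications and blood products share this rule, so no separate blood-product change is needed. The cost is two word changes and a short programming check. Apart from restoring the lost records, the only other effect is that drugs begun during and ended after the on-therapy period are relabelled AFTER, and they remain in the table.
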